**Statistical Methods:**

The following analysis populations will be evaluated: safety, safety (modified), and intent-to-treat exposed (ITT-E). The safety population will consist of all subjects who received the study drug and will be used to assess treatment-emergent adverse events and other safety evaluations based on actual treatment received. A separate safety population, safety (modified), will be created to assess safety excluding subjects who received additional OAB medication at Week 24 or after. ITT-E will be used for demographics, baseline characteristics, and efficacy analyses. The ITT-E population will consist of all subjects randomized and treated from Cohorts 1 and 2.

Interim analyses may be conducted when  $\geq 50\%$  of subjects in Cohort 1 and/or when  $\geq 50\%$  of subjects in Cohort 2 have completed at least 12 weeks of follow-up post-randomization (or prematurely exited the study prior to Week 12) for future planning purposes. A planned interim analysis will be performed to evaluate the objectives of the protocol at Week 12, after all subjects in Cohorts 1 and 2 have completed the Week 12 Visit/Visit 6 (or prematurely exited the study prior to Week 12). The final analysis will be performed after all subjects have completed the study or exit the study prematurely. Details of the interim analyses and final analysis will be described in the Statistical Analysis Plan.

The study has no formal statistical primary endpoint hypothesis. Descriptive statistics will be used to evaluate the efficacy and safety endpoints. For continuous efficacy endpoints, estimates of least squares means, standard error, and 95% confidence intervals (CI) will be presented for each treatment group. Nominal p-values from comparisons to placebo may be provided for descriptive purposes.

The point estimate of the treatment difference and 95% confidence interval for the change from baseline at each visit for each continuous efficacy variable relative to placebo will be analyzed using a mixed-effect model for repeated measures (MMRM) method. The analysis model will include terms for baseline value as a covariate, in addition to the terms for treatment, visit, and treatment by visit interaction. For the urodynamic variables evaluated, only the independent central reviewer's interpretation will be analyzed.

[figure not shown]

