##### 3.2.1. Exploratory Efficacy Endpoints

Exploratory efficacy endpoints include the following:

- Change from baseline at Week 12 in average daily number of UUI episodes
- Change from baseline at Week 12 in average daily number of micturitions
- Change from baseline at Week 12 in average daily number of urinary incontinence (UI) episodes
- Change from baseline at Week 12 in average daily number of urgency episodes
- Proportion of subjects achieving  $\geq 50\%$ ,  $\geq 75\%$ , and 100% reduction from baseline at Week 12 in UUI episodes per day
- Change from baseline at Week 12 in average volume voided per micturition
- Health outcomes parameters:
  - Change from baseline at Week 12 in total summary score from the urinary Incontinence-Specific Quality-of-Life Instrument (I-QOL)
  - Change from baseline at Week 12 in OAB Questionnaire (OAB-q) scores
  - Overall change of bladder symptoms based on the Patient Global Impression of Change (PGI-C) scale score at Week 12

- Urodynamic parameters (read by an independent central reviewer):
  - Cystometric volume at 1st sensation to void (FSV)
  - Maximum cystometric capacity (MCC)
  - Maximum detrusor pressure during the storage phase (corrected PdetMaxStorage)
  - Presence/absence of the first involuntary detrusor contraction (IDC) and, if present:
    - Volume at first IDC (Vol@1stIDC)
    - Maximum detrusor pressure during the first IDC (corrected Pdet@1stIDC)

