### 9.2. Sample Size Determination

For this exploratory study, the sample size was empirically chosen. With a total of 23 evaluable female subjects in each of the URO-902 treatment groups and 23 evaluable female subjects in the placebo group, this study would have approximately 55% power to detect a between-group difference of 1.8 episodes in the mean change from baseline to Week 12 in the number of UUI episodes per day between the URO-902 and placebo treatment groups (based on a 2-sample t-test with a 2-sided type I error rate of 0.05 and standard deviation [SD] of 2.86). Furthermore, the half-width of the confidence interval would be the following for different SD assumptions:

| SD   | N per Group | Half-Width of Confidence Interval | Lower Limit | Upper Limit |
|------|-------------|-----------------------------------|-------------|-------------|
| 2.86 | 23          | 1.70                              | 0.10        | 3.50        |
| 3.00 | 23          | 1.78                              | 0.02        | 3.58        |
| 2.50 | 23          | 1.49                              | 0.31        | 3.29        |

In order to account for subject attrition (approximately 10%), the sample size was increased to 26 subjects for each treatment group, amounting to a total of 78 randomized subjects required for exploratory efficacy analyses in both Cohort 1 ( $n = 39$ ) and Cohort 2 ( $n = 39$ ).

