### **9.5. Statistical Analyses**

#### **9.5.1. Statistical Methods for Efficacy Analysis**

Descriptive statistics will be used to evaluate the efficacy endpoints. For continuous efficacy endpoints, estimates of least squares means, standard error, and 95% confidence intervals (CI) will be presented for each treatment group and the difference between each dose group relative to placebo. Nominal p-values from comparisons from each dose group relative to placebo may be provided for descriptive purposes.

Baseline will be defined as the diary assessments collected prior to randomization for all diary related efficacy endpoints and results of the questionnaires collected at the Day 1 Visit (Visit 3) for all health outcome endpoints.

For the analysis of continuous change from baseline endpoints (eg, change from baseline in average daily number of UUI episodes, change from baseline in average daily number of micturitions, change from baseline in average daily number of UI episodes, change from baseline in average daily number of urgency episodes, change from baseline in average volume voided per micturition, change from baseline in average I-QOL total summary score, change from baseline in OAB-q score, and change from baseline in PGI-C score), a mixed-effect model for repeated measures (MMRM) with restricted maximum likelihood estimation will be used. Analysis will be stratified by the randomization factors assuming there are greater than 5 subjects per stratum. This model corrects for dropout and accounts for the fact that measurements taken on the same subject over time tend to be correlated, by using all available information on subjects within the same covariate set to derive an estimate of the treatment effect for a drop-out free population.

The analysis model for each efficacy endpoint will include terms for treatment, visit, visit by treatment interaction term, and baseline score as covariates. If warranted, non-parametric methods will be used. For interim analyses, analysis of covariance (ANCOVA) may be performed instead of MMRM due to limited sample size. If there is a sufficient sample size, randomization factors will be considered for use in the model. Data for all visits will also be presented.

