6.3. Urodynamic Endpoints

For urodynamic assessments only the independent central reviewer's interpretation will be summarized. The frequency and percentage of central reader's assessment compared to the investigator's reading and descriptive summary of the results of each parameter will be provided for baseline and Week 12. The change from baseline at Week 12 will also be provided.

6.4. hSlo cDNA concentrations

The presence and absence of hSlo cDNA concentrations will be summarized at each protocol specified visit. If present, numeric results of the concentration will also be summarized at each visit.

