14.2.5.2	Summary of Average Volume Voided per Micturition	ITT-E	By-visit Descriptive Summary	TL, EOS
14.2.6.1	Proportion of Subjects Achieving $\geq 50\%$ Reduction in Number of Average Daily Urge Urinary Incontinence Episodes from Baseline	ITT-E	Week 12 first, then other visits sequentially	EOS
14.2.6.2	Proportion of Subjects Achieving $\geq 75\%$ Reduction in Urge Urinary Incontinence Episodes from Baseline	ITT-E	Week 12 first, then other visits sequentially	EOS
14.2.6.3	Proportion of Subjects achieving 100% Reduction in Urge Urinary Incontinence Episodes from Baseline	ITT-E	Week 12 first, then other visits sequentially	TL, EOS
14.2.7.1	Change from Baseline I-QOL Domains (MMRM)	ITT-E	Week 12 first, then Week 6	TL, EOS
14.2.7.2	Summary of I-QOL Scores	ITT-E	By-visit Descriptive Summary	TL, EOS
14.2.7.3	Proportion of Subjects Achieving the Minimally Important Difference in I-QOL Total Summary Score	ITT-E	Week 12 first, then Week 6	EOS
14.2.8.1	Change from Baseline in OAB-q Scores (MMRM)	ITT-E	Week 12 first, then Week 6	TL, EOS
14.2.8.2	Summary of OAB-q Scores	ITT-E	By-visit Descriptive Summary	TL, EOS
14.2.9.1	Change from Baseline on Patient Global Impression Change Score at Week 12	ITT-E	Week 12 only	TL, EOS
14.2.9.2	Summary of Patient Global Impression	ITT-E	By-visit Descriptive summary and change from baseline of numeric score	EOS
14.2.10	Summary of Urodynamic Parameters	ITT-E	Baseline and Week 12 only	EOS
14.2.11	Summary of hSlo cDNA Concentrations	ITT-E		TL, EOS
14.2.12.1	Change from Baseline in Average Daily Number of Nighttime Voids (MMRM)	ITT-E	Week 12 first, then other visits sequentially	EOS

Title		Population	Programming Note	Deliverable
14.2.12.2	Summary of Average Daily Number of Nighttime Voids	ITT-E	By-visit Descriptive Summary	EOS
14.2.13.1	Proportion of Subjects Achieving $\geq 50\%$ Reduction in Number of Average Daily Urinary Incontinence Episodes from Baseline	ITT-E	Week 12 first, then other visits sequentially	EOS
14.2.13.2	Proportion of Subjects Achieving $\geq 75\%$ Reduction in Number of Average Daily Urinary Incontinence Episodes from Baseline	ITT-E	Week 12 first, then other visits sequentially	EOS
14.2.13.3	Proportion of Subjects Achieving 100% Reduction in Number of Average Daily Urinary Incontinence Episodes from Baseline	ITT-E	Week 12 first, then other visits sequentially	EOS
Safety Endpoints				
Adverse Events				
14.3.1.1	Overall Treatment-Emergent Adverse Events	Safety		TL, EOS

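### SAP 6.3 pre-specifies no baseline-adjusted difference from placebo for the continuous urodynamic endpoints, and SAP Section 9 does not record the departure from the protocol

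*SAP*

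**What the plan says.** Protocol 3.2.1 and SAP 1.1.1 list the urodynamic parameters among the exploratory efficacy endpoints, read by an independent central reviewer. They are first-sensation volume (FSV), maximum cystometric capacity (MCC), corrected PdetMaxStorage and presence of a first involuntary detrusor contraction (IDC). Where an IDC is present, Vol@1stIDC and Pdet@1stIDC are added. The efficacy objective in Protocol 3.1 is a comparison with placebo. Protocol 8.2.3 schedules two assessments, baseline and Week 12.

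On analysis, the protocol synopsis (Statistical Methods) says that the treatment difference and 95% CI for "the change from baseline at each visit for each continuous efficacy variable relative to placebo will be analyzed using a mixed-effect model". Protocol 9.5.1 says that, for continuous efficacy endpoints, LS means, standard errors and 95% CIs will be presented "for each treatment group and the difference between each dose group relative to placebo". Both places add a sentence on urodynamics, but it settles only whose reading is used.

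SAP 6.3 plans a comparison of central and investigator readings, a "descriptive summary of the results of each parameter will be provided for baseline and Week 12", and the change from baseline at Week 12. No urodynamic parameter appears in the MMRM list in SAP 6.1 or the stratified risk-difference list in SAP 6.2. SAP 4.2.2 presents urodynamic data by arm only. The single output is Table 14.2.10, "Summary of Urodynamic Parameters", for baseline and Week 12. SAP Section 9 records the changed method for PGI-C and does not mention urodynamics.

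**The concern.** The diary counts, voided volume, I-QOL and OAB-q scores all receive an adjusted difference from placebo with a 95% CI. The urodynamic parameters are the only efficacy endpoints described as centrally read, and they receive none. SAP 1.2.3 states that the intent is to estimate each dose's effect relative to placebo, and SAP 6.1 opens by promising that contrast for continuous efficacy endpoints, so the omission also sits awkwardly within the SAP.

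At stake is the quality of the placebo comparison for these measures. A contrast that is not pre-specified would have to be constructed by the reader, from raw changes, in arms small enough for chance baseline differences to matter. Randomisation offers little protection on this point. Amendment 1 replaced detrusor overactivity with prior onabotulinumtoxinA use as a stratification factor, so Cohorts 1b and 2 are not balanced by design on the finding closest to these endpoints.

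**Working it through.** **1. The plan's own figure.** The documents state power only for UUI episodes. Protocol 9.2 assumes 23 evaluable women on each dose and 23 on placebo, and concludes that "this study would have approximately 55% power to detect a between-group difference of 1.8 episodes". The basis is a two-sided two-sample t-test at the 0.05 level with an SD of 2.86. A two-sample noncentral t calculation with 23 v 23, difference 1.8 and SD 2.86 gives 55.1%, which agrees. The half-width t(0.975, 44) × SD × √(2/23) gives 1.70, 1.78 and 1.49 for SDs of 2.86, 3.00 and 2.50, matching the protocol table. No urodynamic SD or power is given, so what follows is in SD units and takes only the 23 per arm from the plan.

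**2. Does the protocol rule reach urodynamics?** The synopsis rule covers each continuous efficacy variable. FSV, MCC, PdetMaxStorage, Vol@1stIDC and Pdet@1stIDC are continuous and are listed as efficacy endpoints. The MMRM list in Protocol 9.5.1 does not name them, but it is introduced as a list of examples. IDC presence is binary. The protocol gives the CMH method only for UUI responders, so no protocol rule on between-arm comparison applies to it. With one post-baseline visit, the visit and treatment-by-visit terms drop out and the protocol's MMRM reduces to an ANCOVA at Week 12.

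**3. What the planned output still allows.** SAP 4.2.2 gives n, mean and SD by arm for continuous variables, and SAP 6.3 adds change from baseline. From these a reader can form the dose-minus-placebo difference in mean change and its 95% CI. With 23 v 23 the half-width is t(0.975, 44) × √(2/23) = 0.59 SD of change.

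**4. What adjustment adds.** Assume equal SD at baseline and Week 12, and correlation ρ between them. In units of that SD:
- SD of raw change = √(2(1 − ρ))
- residual SD under ANCOVA = √(1 − ρ²)
- variance ratio = (1 − ρ²) / (2(1 − ρ)) = (1 + ρ)/2
- half-width = t(0.975, 66) × SD × √(2/23) = 1.997 × 0.295 × SD = 0.589 × SD, with 66 = 3 × 23 − 3 because all three arms are fitted. The few degrees of freedom spent on covariates are ignored.

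| Assumed ρ | Variance ratio | Raw-change half-width | ANCOVA half-width |
|---|---|---|---|
| 0.3 | 0.65 | 0.589 × 1.183 = 0.70 | 0.589 × 0.954 = 0.56 |
| 0.5 | 0.75 | 0.589 × 1.000 = 0.59 | 0.589 × 0.866 = 0.51 |
| 0.7 | 0.85 | 0.589 × 0.775 = 0.46 | 0.589 × 0.714 = 0.42 |

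The difference in variance comes from chance baseline imbalance. A baseline gap of d between arms moves the raw-change contrast by (1 − ρ)d in the opposite direction. One standard error of d is √(2/23) = 0.295 SD, so a gap of that size moves the contrast by 0.7 × 0.295 = 0.21, 0.5 × 0.295 = 0.15 or 0.3 × 0.295 = 0.09 SD. Protocol 8.2.3 accepts a historical baseline study up to 90 days before screening. If that lowers ρ, adjustment matters more.

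**5. Parameters tied to an IDC.** Vol@1stIDC and Pdet@1stIDC exist at Week 12 only for subjects who have an IDC then, a subset formed after randomisation that treatment may itself alter. If 30%, 50% or 70% of subjects contributed (assumed; 7, 12 or 16 per arm), the unadjusted half-width would be about 1.16, 0.85 or 0.72 SD. For IDC presence at an assumed 30% to 70%, 1.96 × √(2p(1 − p)/23) gives about 26 to 29 percentage points.

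**The case against.** The strongest reply is that the protocol is not as clear as the synopsis sentence suggests. Protocol 3.2.1 lists the urodynamic parameters without a change or a timepoint, unlike the diary and questionnaire scores. Protocol 9.5.1 names no urodynamic variable in its MMRM examples. The synopsis model has visit terms that cannot be fitted with one post-baseline visit. The protocol also calls its efficacy evaluation descriptive, states no formal hypothesis and leaves full detail to the SAP. On that view SAP 6.3 is a permissible choice that was simply not documented.

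Part of this stands. The protocol contains a general rule that was never reconciled with these endpoints, rather than an explicit urodynamic instruction. But the rule is broad, nothing exempts urodynamics from it, and the same descriptive framework still gives the other continuous endpoints an adjusted difference with CI. Estimating a difference needs no formal hypothesis.

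Three stronger readings are tempting and are not supported:
- A reader might infer that the urodynamic data cannot answer the placebo question, or yield no estimate of effect. The per-arm statistics allow an unadjusted difference and CI.
- A reader might infer that the protocol conflict includes IDC presence. The protocol sets no between-arm method for it.
- A reader might infer that regression to the mean biases the comparison. No eligibility criterion sets a threshold on FSV, MCC or detrusor pressure, and in expectation regression to the mean affects randomised arms equally. Only chance imbalance remains.

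**Conclusion.** The point holds in a limited form. For the continuous urodynamic endpoints the SAP pre-specifies no baseline-adjusted placebo difference with a 95% CI, the protocol's general rule calls for a difference and CI, and the departure is not recorded. The consequence is lower precision and exposure to chance baseline imbalance, not loss of the comparison.

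The size is the gain from adjustment: 0.14, 0.08 or 0.04 SD off the half-width at correlations of 0.3, 0.5 and 0.7. It rests on assumed correlations, equal variances at the two visits and 23 evaluable subjects per arm. It does not measure the cost of having no planned contrast, which the documents give no basis to quantify. In an exploratory study without a primary hypothesis this is a modest defect, worth correcting because the remedy needs no new data.

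**What to change.** In SAP 6.3, add for FSV, MCC and corrected PdetMaxStorage a Week 12 ANCOVA of change from baseline on treatment, baseline value and the two stratification factors, subject to the SAP 6.1 rule on small strata. Report the LS mean difference of each dose from pooled placebo with 95% CI in one added table. SAP 6.1 already uses ANCOVA as a sensitivity analysis for UUI episodes and micturitions, so no new method is introduced.

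Keep Vol@1stIDC and Pdet@1stIDC descriptive, and state in SAP Section 9 that this departs from the protocol's general rule because the contributing subset is defined after randomisation.

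Optionally, as an addition and not to repair a protocol conflict, report a Week 12 risk difference with 95% CI for IDC presence among subjects with a Week 12 reading. The SAP 4.2.3 convention that counts missing as non-response was written for responder endpoints and should not be carried over.

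If the sponsor prefers description only, the minimum is an entry in SAP Section 9 that records and justifies it. The cost is SAP wording and one table; baseline and Week 12 readings are already collected.

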7. SAFETY ANALYSIS

The safety population will be used for all safety analyses. Safety will be based on adverse events reporting, clinical laboratory data, ECGs, PVR, physical examinations, and vital signs. No inferential statistical testing is planned on the safety data, all data will be descriptively summarized by treatment and visit.

7.1. Extent of Exposure and Compliance

Since this is a treatment with single injection at the start of the study, no summary of exposure or compliance will be provided. A listing of study injection will be provided for all subjects in the safety population.

7.2. Adverse Events

Adverse events (AEs) will be coded using MedDRA version 22.1. or later.

All reported AEs (whether treatment emergent or not) will be included in by-subject AE listings. Sorting will be by treatment, subject, date of event, SOC, PT and then verbatim description.

An AE will be considered a treatment emergent adverse event (TEAE) if it begins or worsens in severity after initial exposure of the study treatment through 48 weeks after treatment administration or the date of the initiation of another OAB medication, investigational agent or surgical intervention, whichever occurs first. The determination of "48 weeks" will be based on the study day of the AE start date instead of the visit date of the Week 48 visit. The OAB medication will be determined based on the checkbox "Is this an additional OAB medication"

on the concomitant medication CRF. After data are collected and reviewed by the clinical team, a blinded list of investigational agents and surgical interventions will be provided to the programming team prior to database lock to determine which AEs should no longer be considered treatment emergent due to possible confounding effects. Partial AE start dates will be imputed as detailed in [Section 4.2.3](#).

Summary tables will be based on TEAEs. The incidence of TEAEs will be presented using counts and percentages of subjects with TEAEs and tabulated by SOC and PT. SOC will be sorted in descending frequency and PT within SOC will be sorted by descending frequency based on the incidence of all subjects treated with URO-902 included in the summary. If a subject has multiple occurrences (start and stop) of an event associated with a specific SOC or PT within a SOC, a subject will only be counted once in the incidence count for the SOC or PT within SOC respectively.

An overall summary table of AEs by treatment group will be presented detailing the number and percentage of subjects, and number of events for the following categories:

- At least one TEAE;
- At least one Treatment-Related TEAE;
- At least one Grade ≥ 3 TEAE (Mild = Grade 1, Moderate = Grade 2, Severe = Grade 3, Life-Threatening = Grade 4, Death = Grade 5)
- At least one Grade ≥ 3 Treatment-Related TEAE;
- At least one Serious TEAE;
- At least one Serious Treatment-Related TEAE;
- At least one TEAE leading to Discontinuation from Study;
- At least one TEAE of Special Interest;
- At least one Treatment-Related TEAE of Special Interest

Except for all TEAEs which will be summarized by SOC and PT, the incidence of all other TEAEs by PT will be presented for the following in descending frequency based on the incidence of all subjects treated with URO-902.

- All TEAEs by SOC and PT;
- All TEAEs
- Treatment-related TEAEs (i.e., Possibly Related or Probably Related);
- All TEAEs by PT, and maximum severity (where the maximum intensity per subject will be counted at each level of summarization);
- TEAEs with Grade ≥ 3 ;

- Treatment-related TEAEs with Grade ≥ 3 ;
- Serious TEAEs;
- Treatment-related serious TEAEs;
- Fatal TEAE;
- TEAEs leading to discontinuation from study;
- TEAE of Special Interest;
- Treatment-related TEAE of Special Interest;
- Non-fatal serious TEAE;

An AE is considered an AE of Special Interest if on the AE eCRF the answer to the item “Is this an AE of Special Interest?” is “Yes”. For specific criteria used to identify AEs of Special Interest refer to section 8.5.6 of the protocol.

Overall AE listing will include the treatment arm, start and stop dates/times of the AE, treatment dates/times, and treatment emergent status.

A Treatment related AE is defined as an AE for which the investigator classifies the AE as being “Possibly Related” or “Probably Related” to study treatment on Adverse Event eCRF. Missing relationship and severity (intensity) will be imputed per [Section 4.2.3](#).

Additional summary table will be provided for AEs that occurred on or after the study dose through 48 weeks after the study dose administration and after additional OAB medication was taken, or initiation of investigational agent, or surgical intervention.

The following additional listings will be provided:

- Listing of deaths
- Listing of SAEs
- Listing of TEAEs of Special Interest
- Listing of TEAEs leading to study discontinuation

